8) Mortality, including 3-day mortality (within 3 days of transfer) and inhospital mortality (secondary outcome)

9) Intermediate process outcomes, including presence, timeliness and completeness of accept note as measured by frequency of accept note availability at time of IHT patient arrival and frequency of inclusion of prespecified data elements (secondary outcome)

Statistical Methods and Analytic Plan: All outcomes will be compared postversus pre-implementation via ITS methodology, allowing us to evaluate for statistically significant changes in outcomes while accounting for baseline trends. Multivariable analyses will be utilized to adjust for potential confounders.

Covariates: Potential confounders will be collected via administrative sources and include basic patient demographics (age, gender, race, ethnicity), insurance, diagnosis category (using standard ICD-10 grouper algorithms on the principal problem on the Hospital Problem List on admission, which we have found to be more accurate than the billing diagnosis on admission), comorbidity (i.e., Elixhauser score), illness severity (eCART score on admission, which uses vital sign and laboratory data to predict cardiac arrest, ICU transfer, or death among hospitalized patients),36 clinical service at time of admission, and time of year of transfer (by quarter) to adjust for training effects on residents and seasonal case mix. To avoid over-testing, all patient characteristics will be entered into the analysis model. Nonsignificant collinear terms will be removed from the final models.

Subgroup analysis: We will conduct a limited number of a priori subgroup analyses to evaluate for differential effect of the intervention in different sub-populations of transferred patients by using interaction terms (subgroup*intervention) to determine effect modification. Specifically, we will stratify analyses by: 1) admitting service (GMS, cardiology, oncology, medical/cardiac ICU); 2) diagnosis category; and 3) severity of illness on admission (using the eCART score as described above).

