Statistical techniques: For all analyses we will use a segmented regression analysis on all eligible patients, evaluating outcomes monthly during the preimplementation and post-implementation periods (after the 3-month "washin" period). This approach quantifies both a "step" change in the level of outcome and a "slope" change in the trend of outcome. For our primary outcome (number of clinician-reported medical errors per patient), we will use multivariable Poisson regression models (SAS v9.4 statistical package, Cary, NC). For adverse events, preventable and ameliorable adverse events, and other dichotomous outcomes (rapid response/code, ICU-transfer, mortality, presence of accept note) we will use multivariable logistic regression models. For LOS, given its skewed nature we will use a multivariable generalized linear regression model assuming a gamma distribution with a log-link. We will use descriptive statistics to evaluate timeliness of accept note availability and inclusion of accept note data elements. For all analyses, the transfer episode will serve as the unit-ofanalysis.

Outcomes reporting: Patient and transfer process characteristics will be presented descriptively using means with standard deviations, medians with

inter-quartile ranges, and proportions with 95% confidence intervals as appropriate. Each outcome will be reported as crude as well as adjusted and clustered effects with 95% confidence intervals. All analyses will be on an intention-to-treat basis. Two-sided p values < 0.05 will be considered significant. All analyses will be conducted using SAS (SAS v9.4 statistical package, Cary, NC).

Power and sample size: Based on previous data, we estimate a baseline rate of 25 reported medical errors per 100 patient transfers. With an alpha of 0.05, we will require an effective sample size of approximately 594 patient transfers during the 9-month pre-implementation period and 594 patients transfers during the 9-month post-implementation period to have 80% power to detect a 30% relative reduction to 17.5 errors per 100 patient transfers, as has been observed in similar studies. Assuming 1,848 total patient transfers to GMS, cardiology, oncology and medical/cardiac ICU services at BWH per year (1,368 per 9-months, internal data), while allowing for missed days of survey administration (i.e., during holidays), and accounting for a survey response rate of 90% (based on similar studies), we should easily achieve this sample size.

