Given the large number of different clinicians likely to admit these patients across all services over the 18 months of data collection, the cluster size is likely negligible, therefore resulting in an effective sample size close to the actual sample size.

Briefly describe study procedures. Include any local site restrictions, for example, "Subjects enrolled at Partners will not participate in the pharmacokinetic portion of the study." Describe study endpoints.

Please see detailed description of study procedures above.

All study procedures will take place at BWH. There are no local site restrictions for the procedures described in this study.

For studies involving treatment or diagnosis, provide information about standard of care at Partners (e.g., BWH, MGH) and indicate how the study procedures differ from standard care. Provide information on available alternative treatments, procedures, or methods of diagnosis.

Current practices for inter-hospital transfer of patients to GMS, cardiology, oncology and medical/cardiac ICU services at BWH involves an expectation of documentation of clinical information in advance of patient transfer. However, this documentation is largely non-standardized and involves a

diffuse group of clinicians who are responsible for both accepting the patient for transfer and are expected to document the patient accept note. For example, for GMS patient transfers, this responsibility for accepting patients for transfer and documenting their accept note falls to any of the over 50 hospitalist faculty who rotate weekly on the clinical service. This diffusion of responsibility is similar for cardiology, oncology and ICU service patient transfers as well. Collectively, these practices result in variable presence, timeliness and quality of accept note documentation in advance of patient transfer.

We expect (our hypothesis) is that implementation of this standardized accept note, as well as centralization of accept note documentation, will be a marked improvement over current standard of care – leading to both improved frequency of documentation and quality of documentation. However, we do not know this for sure – that is why we are conducting the study. In other words, there is equipoise.

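### The protocol promises a trend-adjusted comparison for every outcome but only describes accept-note completeness, and possibly timeliness, although better documentation quality is part of its hypothesis

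*Protocol*

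**What the plan says.** Item 9 under Primary and Secondary Outcome Measures is a secondary outcome: "Intermediate process outcomes, including presence, timeliness and completeness of accept note". It is to be "measured by frequency of accept note availability at time of IHT patient arrival and frequency of inclusion of prespecified data elements".

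Three general rules cover it:

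- Statistical Methods and Analytic Plan: "All outcomes will be compared postversus pre-implementation via ITS methodology".
- Statistical techniques: "For all analyses we will use a segmented regression analysis on all eligible patients", with both a step and a slope change quantified.
- Outcomes reporting: "Each outcome will be reported as crude as well as adjusted and clustered effects with 95% confidence intervals".

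Statistical techniques then assigns a method to each outcome. Presence of the note is placed with the dichotomous outcomes: "rapid response/code, ICU-transfer, mortality, presence of accept note) we will use multivariable logistic regression models". The other two components are treated differently: "We will use descriptive statistics to evaluate timeliness of accept note availability and inclusion of accept note data elements".

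The standard-of-care section gives the investigators' hypothesis for the intervention, "leading to both improved frequency of documentation and quality of documentation".

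**The concern.** The three general rules and the descriptive-statistics sentence cannot all hold for item 9. The protocol is not silent on the method, so this is not a detail left to a later analysis plan. It fixes a method that breaks its own rules, and an analyst who follows one sentence breaches another.

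The part left without a model is the part closest to the template. The intervention has two components: a standardized note (Aim 2a) and a move of documentation to Access Center nurses (Aim 2b). Presence could rise through the move of responsibility alone, whereas completeness shows whether the content of the notes changed. If the primary result is null, a reader will want to know whether note content shifted beyond its earlier course. If it is positive, the same question bears on why.

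The design was chosen to separate an intervention effect from a baseline trend. A descriptive contrast of two periods does not do that. A trend is conceivable, because a structured note had already been introduced for general medical transfers and that pilot already included the move to nurses (Aims 1 and 2). The documents do not show that a trend exists.

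**Working it through.** **1. Which component gets which analysis**

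| Component of item 9 | Measure given | Covered by the ITS and adjusted-effect rules | Method assigned |
|---|---|---|---|
| Presence | Availability at arrival, if this is what presence means | Yes | Segmented logistic regression |
| Timeliness | Availability at arrival | Yes | Descriptive |
| Completeness | Inclusion of prespecified elements | Yes | Descriptive |

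The measurement sentence gives two measures for three components. If the modelled presence variable is availability at arrival, the core of timeliness is modelled under another name. If presence means that a note exists at any time, timeliness is not modelled. Completeness has no model under either reading.

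**2. The plan's own sample size**

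No figure is given for the process outcomes. The only one is 594 transfers per period for the primary outcome. A two-sample Poisson rate comparison (unpooled variance, two-sided 0.05, 80% power) gives

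n = (1.960 + 0.842)² × (0.25 + 0.175) / (0.075)² = 593.03, rounded up to 594.

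The figure reproduces, and nothing in this point changes it.

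**3. What a pooled pre/post table could absorb (illustration)**

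Inputs: 9 months before, 3 months of wash-in and 9 months after. The period midpoints are 4.5 + 3 + 4.5 = 12 months apart. The monthly drift is an assumption, since the documents give neither a baseline nor a trend.

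- 0.5 points a month: 12 × 0.5 = 6 points
- 2 points a month: 12 × 2 = 24 points

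Either would look like improvement with no intervention effect. With no drift the distortion is zero.

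**4. Whether a segmented model is feasible**

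Inputs: 1,848 / 12 = 154 transfers a month, with pre months numbered 0 to 8 and post months 12 to 20. Assumptions: linear-probability approximation, equal monthly numbers, no autocorrelation, and one yes/no observation per transfer.

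The step is the post line at month 12 minus the pre line carried forward to month 12. Within each period the sum of squared deviations of month from its mean is 60. In units of the monthly variance:

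- post line at its first month: 1/9 + 4²/60 = 0.378
- pre line carried to month 12: 1/9 + 8²/60 = 1.178
- total: 1.556
- simple pre/post difference: 1/9 + 1/9 = 0.222
- ratio: 1.556 / 0.222 = 7

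The trend-adjusted step therefore has 7 times the variance of the simple difference. With p̄ the mean of the two rates, SE = √[p̄(1 − p̄)/154 × 1.556] and power = Φ(step/SE − 1.96). For 50% to 60%, p̄ = 0.55, SE = 0.050 and power = Φ(2.00 − 1.96), about 52%.

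| Assumed change | Power, segmented step |
|---|---|
| 50% to 60% | 52% |
| 60% to 70% | 55% |
| 70% to 85% | 95% |
| 50% to 70% | 98% |
| 60% to 80% | 99% |

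The simple comparison exceeds 99% in every row, but only because it assumes that there is no trend.

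**The case against.** The best defence reads the general sentences as an overview and the method-by-method paragraph as the operative text. On that reading the authors deliberately chose description for two parts of an intermediate process measure. Aim 3 lists only patient safety outcomes, and describing process measures is a legitimate choice. Narrowing the general wording would then be enough. Part of this stands: narrowing would remove the contradiction. It would still leave the quality half of the hypothesis without a trend-adjusted estimate in a design adopted to provide one.

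Three further points stand and limit the concern. Presence is modelled, and timeliness may be covered through it. Descriptive results could be tabulated by month, since outcomes are to be evaluated monthly, and such a table would make an earlier trend visible without estimating an effect net of it. The 6 to 24 points are only the assumed drift multiplied by 12, and the earlier pilot on one service could just as well have left a higher but stable baseline.

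A reader might infer that the trial cannot test its own mechanism. The documents do not support that. The frequency half of the hypothesis has a segmented model with baseline trend, step and slope, so for presence a secular rise can be separated from an implementation effect. Nor would modelling completeness establish mechanism: it would show whether the intervention was delivered.

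**Conclusion.** The inconsistency is real and rests on the text alone. Completeness gets no trend-adjusted estimate, and neither does timeliness unless presence means availability at arrival. This conflicts with the protocol's rules for all outcomes and leaves the quality part of its hypothesis described only.

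The consequence is moderate. One secondary process outcome is affected. The primary outcome and its model, the sample size, the patient safety outcomes and the test of note presence are untouched. The possible bias in a pooled contrast cannot be sized from the documents, so the 6 to 24 points illustrate an assumed drift and are not an estimate. The power figures also depend on assumed rates and on ignoring autocorrelation. They suggest that a segmented analysis is informative for changes of about 15 to 20 points and weak for about 10. The change is worth making because it is cheap and the conflict is with a stated method.

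**What to change.** In Statistical techniques, replace the descriptive-statistics sentence as follows:

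- **Availability.** Define the modelled binary outcome as note available at patient arrival (yes/no) and analyse it by segmented logistic regression, as for the other dichotomous outcomes. This also settles what presence means.
- **Completeness.** Fix one endpoint: the number of prespecified elements included out of the total. Analyse it by segmented binomial regression allowing for overdispersion, because elements of the same note are correlated.
- **Absent notes.** Include all eligible transfers and count an absent note as zero elements. Scoring only existing notes would select on something the intervention is expected to change. Add a sensitivity analysis among transfers with a note, because the main endpoint mixes presence with content.
- **Reporting.** Give step and slope estimates with 95% confidence intervals, and keep monthly descriptive tables as a supplement.

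If the investigators prefer description, the minimum is to narrow the general sentences and label these components descriptive. That removes the contradiction but not the gap.

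The cost is a little more analysis, with no new data. Precision for modest changes will be limited, at about 52 to 55% power for a 10-point step under the assumed rates. Interpretation should therefore rest on the estimates and their intervals, and a non-significant step should not be read as no change.

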Describe both the expected benefits to individual subjects participating in the research and the importance of the knowledge that may reasonably be expected to result from the study. Provide a brief, realistic summary of potential benefits to subjects, for example, "It is hoped that the treatment will result in a partial reduction in tumor size in at least 25% of the enrolled subjects."

Indicate how the results of the study will benefit future patients with the disease/condition being studied and/or society, e.g., through increased knowledge of human physiology or behavior, improved safety, or technological advances.

This project will advance the field by investigating a strategic intervention aimed at reducing known contributors to patient harm: sub-optimal communication and clinical information exchange within IHT, an understudied high-risk care transition. Additionally, if shown effective at reducing patient harm, the standardized accept note developed from this study can be adapted and used by other CRICO-insured institutions to address potential harm and malpractice risk related to IHT.

Given previous data that estimates an approximate baseline rate of 25 reported medical errors per 100 patient transfers, our anticipated sample size will be more than enough to have 80% power to detect a 30% relative reduction to 17.5 errors per 100 patient transfers, as has been observed in similar studies.

Impact on Department, Institution/Organization, and CRICO-wide Membership: If shown effective, our findings will provide convincing evidence that this intervention can and should be adapted for use among other CRICO-insured institutions to address potential harm and malpractice risk related to IHT. Importantly, the standardized accept note developed for this study will be generally accessible within the EHR (Epic). This has critical implications for future dissemination of this work, as this central accessibility will allow for easy modification and expansion to other services at BWH and all other Partners hospitals interested in mitigating patient safety risk during IHT, either via individual departmental efforts or as part of an organizational strategy to address this risk. Moreover, these interventions could be easily adapted for other CRICO member hospitals (e.g., note templates are part of all EHRs, not just Epic).

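### The 594 transfers per period and 80% power belong to an unadjusted two-rate Poisson comparison; under the planned trend-adjusted segmented regression, about 1,247 surveyed transfers per period give only about 25% to 53% power for a 30% step

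*Protocol*

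**What the plan says.** Under Aim 3, Power and sample size, the Protocol starts from a past rate: "we estimate a baseline rate of 25 reported medical errors per 100 patient transfers". It continues: "With an alpha of 0.05, we will require an effective sample size of approximately 594 patient transfers during the 9-month pre-implementation period", with the same number after implementation, "to have 80% power to detect a 30% relative reduction to 17.5 errors per 100 patient transfers". It takes the available volume as 1,848 transfers a year, "1,368 per 9-months, internal data", with 90% survey response, and concludes that the target is easily met. Expected Benefits repeats the claim: "our anticipated sample size will be more than enough to have 80% power to detect a 30% relative reduction".

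The only design allowance is for clustering by admitting clinician. That is judged negligible, "therefore resulting in an effective sample size close to the actual sample size".

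The planned analysis is set out separately. Statistical Methods and Analytic Plan compares all outcomes by interrupted time series, "allowing us to evaluate for statistically significant changes in outcomes while accounting for baseline trends". Statistical techniques says: "For all analyses we will use a segmented regression analysis on all eligible patients". It uses monthly outcomes, leaves out the 3-month wash-in, and estimates both a change in level and a change in slope. The primary outcome, errors per patient, is modelled by Poisson regression.

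**The concern.** The sample size paragraph has the form of a simple before-and-after comparison of two rates, whereas the analysis separates the intervention effect from a time trend. In a single-site series with one switch date, the before/after indicator is strongly correlated with calendar time, so adjusting for trend costs a great deal of precision. Nothing in the power paragraph allows for this, and its remark on effective sample size concerns clustering only.

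The power claim supports the primary outcome and is made twice, in confident terms. If it is wrong for the planned model, a non-significant step would be read as a negative finding from a well-powered study, when the study had little chance of showing the effect it was designed around.

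**Working it through.** **Inputs, all from the Protocol.** Rates 0.25 and 0.175 errors per transfer (rate ratio 0.70), alpha 0.05 and 80% power from Power and sample size; two-sided testing from Outcomes reporting; 9 months before and 9 after from Research Design and Methods; the 3-month wash-in from Aim 2; 1,848 transfers a year and 90% response from Power and sample size.

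**1. Reproducing 594.** For two Poisson rates, n = (1.960 + 0.842)² × (0.25 + 0.175) / (0.25 − 0.175)² = 7.849 × 0.425 / 0.005625 = 593.03, rounded up to 594. Simulating that two-group test at 594 per period gives 80.3% power. The arithmetic is right for a test with no time terms.

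**2. Expected sample.** 1,848 × 9/12 = 1,386 per period, and 2 × 1,386 = 2,772, the total given in Research Design and Methods. The printed 1,368 is a slip. At 90% response, 1,386 × 0.9 = 1,247 (1,368 × 0.9 = 1,231). The surplus over 594 is 1,247 / 594 = 2.1. Expected errors are 1,247.4 × 0.25 = 311.9 before and 1,247.4 × 0.175 = 218.3 after.

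**3. Crude contrast at 1,247.** The variance of the log rate ratio is 1/311.9 + 1/218.3 = 0.00779, so the SE is 0.088. With |ln 0.70| = 0.3567, power is Φ(0.3567/0.088 − 1.960), about 98%.

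**4. Segmented model at 1,247.** The terms are intercept, month, step and slope change. The step at month r is the distance between the two fitted lines at r. Nine equally spaced months have variance 60/9 = 6.667. With flat true trends,

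Var(step) = [1 + (r − m₁)²/6.667]/311.9 + [1 + (m₂ − r)²/6.667]/218.3,

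where m₁ and m₂ are the mean months of the two periods. With the wash-in kept on the time axis, the months are 1–9 and 13–21, so m₁ = 5 and m₂ = 17. With it removed they are 1–18, so m₂ = 14. Power = Φ(0.3567/SE − 1.960).

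| Time coding | Pre factor | Post factor | SE | Variance ÷ crude | Power |
|---|---|---|---|---|---|
| Wash-in kept, step at first post month (13) | 10.60 | 3.40 | 0.223 | 6.4 | 36.0% |
| Wash-in kept, step at month 10 | 4.75 | 8.35 | 0.231 | 6.9 | 33.8% |
| Wash-in kept, step at month 9.5 | 4.04 | 9.44 | 0.237 | 7.2 | 32.5% |
| Wash-in kept, step at mid post-period (17) | 22.60 | 1.00 | 0.278 | 9.9 | 25.0% |
| Wash-in removed, step at month 10 of 18 | 4.75 | 3.40 | 0.176 | 4.0 | 52.9% |

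For the first row: 10.60/311.9 + 3.40/218.3 = 0.0340 + 0.0156 = 0.0496, whose square root is 0.223. A 2.1-fold surplus cannot cover a 4- to 10-fold variance increase.

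**5. Checks on the range.**
- At 594 per period: 20% with the step at the first post month, 14% to 29% across codings.
- At 1,231 per period: within 1 point of the values at 1,247.
- With all 1,386 transfers surveyed: 39% at the first post month and 57% at best.
- One common trend and a step only (no slope change), at 1,247: 37% with the wash-in kept, 53% with it removed.
- Joint two-degree-of-freedom test of step and slope, at 1,247: 29% and 43%.
- Simulated Poisson counts at 1,247 (3,000 runs per setting): 36.0% (first post month), 31.9% (month 9.5), 24.8% (mid post-period), 53.0% (wash-in removed).

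**6. What the sample can detect.** A step has 80% power when |ln RR| = 2.80 × SE. At 1,247 this is about a 48% reduction with the step at the first post month: post errors fall to 162, the SE is 0.234, and 1 − exp(−2.80 × 0.234) = 0.48. With the wash-in removed it is about 40%. Reaching 80% power for a 30% step would need about 3,815 and 2,371 surveyed transfers per period respectively.

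**The case against.** The Protocol powers a fall in the period rate from 25 to 17.5 per 100. It does not say that this fall is the step coefficient, and the time coding may be settled in a statistical analysis plan that is not shown. This part stands: the exact figure depends on choices the Protocol does not state, so a range is the honest answer. It does not rescue the 80%, because no coding tried, nor the step-only model, nor the joint test, comes near it.

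Crude effects will also be reported (Outcomes reporting), and for the crude contrast 594 is correct and 1,247 gives about 98%. That is true, and it offers one acceptable repair. But the analytic plan names the trend-adjusted comparison as the way change is judged, so the crude contrast cannot carry the power claim without saying so.

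The Covariates paragraph allows non-significant collinear terms to be dropped. If that covered the time terms, simulated power under flat trends would rise to about 93% to 94%. The sentence follows one about entering patient characteristics, however, and most naturally refers to those. Dropping the trend terms would also defeat the stated purpose of the design, and it raised the false-positive rate to about 8% to 9%.

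Finally, the fix changes no outcome, model or patient exposure. That keeps its cost low but does not make the claim correct.

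**Conclusion.** The concern holds. The 594 is exact for a two-rate comparison and does not apply to the planned model. At the anticipated 1,247 surveyed transfers per period, power for a true 30% step is 25% to 34% or 36% with the wash-in kept on the time axis, depending on step placement, and 53% with it removed. The step detectable with 80% power is about 48% with the step at the first post month and about 40% in the most favourable coding, against the 30% stated. The shortfall comes from adjusting for trend, not from the slope-change term.

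The results assume equal monthly volumes, a constant step, no true trend, and no covariates, clustering or overdispersion. Overdispersion would lower power, and so would missed survey days: with the step at the first post month, a survey yield of 80% (1,109 per period) gives 33%, and 70% (970) gives 29%. The planned quarter-of-year terms could cost much more. In the one calendar alignment tried, power fell below 10%, but the alignment is not stated, so this is only indicative. The 1,368 slip does not affect the conclusion.

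**What to change.** In Power and sample size and in Expected Benefits, replace the 80% power and sufficiency statements with the power of the contrast that will decide the primary outcome. Name that contrast (step, slope or both), where the step is placed, and whether the wash-in months stay on the time axis.

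For one coding, as an example only: with the step at the first post-wash-in month and the wash-in kept on the time axis, about 1,247 surveyed transfers per period give about 36% power for a 30% step reduction and 80% power for about a 48% step reduction, before covariates, clustering and overdispersion.

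Alternatively, state plainly that 594 and 80% refer only to the crude post/pre rate comparison, which does not account for baseline trend.

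In either case, correct 1,368 to 1,386.

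The cost is Protocol wording and a less favourable power statement. No extra patients are needed, since all eligible transfers are already included.
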